## **9.4 Collection and Shipping of Tissue Specimen(s)**

Collection, Processing and Handling of Archived Specimens: For each resection, all H&E slides shall be made available. In addition 1 FFPE block shall be forwarded to the address within 30 days after patient enrollment. If an institution is unable to provide a tissue block, 20 unstained slides five-micron sections mounted on charged glass slides will be required. Slides will need to be cut with a new blade and using a fresh water bath to avoid contamination. Label the slides with patient ID number, accession number, and order of sections (*include thickness of section if applicable*). Do not bake or place covers slips on the slide.

Shipping of Tissue Specimen(s): Shipment on Monday through Thursday by overnight service to assure receipt is encouraged. Do not ship specimens on Fridays or Saturdays.

**9.5 Collection and Shipping of Blood Specimen(s)**

Shipping of Blood Specimen(s): Collect two 10 mL of venous blood at pre-registration and then two 10 mL every 6 weeks in lavender top (EDTA anticoagulant) vacutainer tube(s). The tubes should be inverted approximately 8-10 times to mix the EDTA. Refrigerate (please do not freeze) sample until shipping. The sample should be placed in a biohazard bag and shipped according to IATA guidelines within 2-3 hours of the blood being drawn on a cold pack (please do not use dry ice). For DFCI samples, call the MGH operator at [contact], ask to page [[name]](#) and [[name]](#), and leave a brief message indicating that the sample has been shipped. For any questions regarding samples, please contact [name] and/or [name].

When samples are shipped and for any concerns regarding shipments, please page [name] at [name].

[name] Lab  
[name]  
Simches Research Center  
[name]  
[name]

**10. STUDY CALENDAR**

Scans and x-rays must be done  $\leq 3$  weeks prior to the start of therapy. All eligibility labs are to be drawn within 14 days of day 1 (as stated in section 3.1.9). Assessments must be performed prior to administration of any study agent. Study assessments and agents should be administered within  $\pm 3$  days of the protocol-specified date, unless otherwise noted.

Trial Period:	Screening Phase a	Treatment Cycles (21 day cycles) b,c								End of Treatment d	Post-Treatment		
Treatment Cycle/Title:	Study Screening (Visit 1)	1	2	3	4	To be repeated beyond 8 cycles v				Discon	Safety Follow-up e	Active Followup f	Longterm Followup g
Scheduling Window (Days):	-14 to 0		± 3	± 3	± 3	± 3	± 3	± 3	± 3				
Administrative Procedures													
Informed Consent h	X												
Inclusion/Exclusion Criteria i	X												
Demographics and Medical History j	X												
Prior and Concomitant Medication Review k	X												
Pembrolizumab Administration		X	X	X	X	X	X	X	X				
Post-study anticancer therapy status f										X	X	X	X
Survival Status g												X	X
Clinical Procedures/Assessments													
Review Adverse Events l	X	X	X	X	X	X	X	X	X	X	X	X	
Full Physical Examination m	X	X	X	X	X	X	X	X	X	X	X	X	
Vital Signs and Weight n	X	X	X	X	X	X	X	X	X	X	X	X	
ECOG Performance Status o	X	X	X	X	X	X	X	X	X	X	X	X	
Laboratory Procedures/Assessments: analysis performed by LOCAL laboratory													
Pregnancy Test – Urine or Serum β-HCG p	X												
PT/INR and aPTT q	X									X			
CBC with Differential r	X	X	X	X	X	X	X	X	X	X			
Comprehensive Serum Chemistry Panel s	X	X	X	X	X	X	X	X	X	X			
TSH t	X	X	X		X		X		X	X			
Efficacy Measurements													
Tumor Imaging u	X			X		X		X		X			
Tumor Biopsies/Archival Tissue Collection/Correlative Studies Blood													
Archival Tissue w	X												

Trial Period:	Screening Phase a	Treatment Cycles (21 day cycles) b,c								End of Treatment d	Post-Treatment		
Treatment Cycle/Title:	Study Screening (Visit 1)	1	2	3	4	To be repeated beyond 8 cycles v				Discon	Safety Follow-up e	Active Followup f	Longterm Followup g
Scheduling Window (Days):	-14 to 0		± 3	± 3	± 3	± 3	± 3	± 3	± 3	At time of Discon	30 days post discon	Every 6 weeks	Every 3 months
Research Blood x	X	X		X		X		X		X			

aAll screening procedures to be performed within 14 days of start of study treatment, except scans which can be obtained within 21 days of starting study treatment, and informed consent may occur up to 28 days prior to start of study treatment

bC1D1 and Day 1 of subsequent cycles: For C1D1 screening assessments may serve as day 1 assessments if performed within 7 days before start of study treatment, except serum pregnancy (within 72 hours of drug) and except in the event that there are any indications that the participant's condition is deteriorating for which laboratory evaluations should be repeated within 48 hours prior to initiation. C1D1 labs must meet eligibility criteria. For all subsequent cycles, required assessments should be performed within 3 days of scheduled cycle day 1.

cStudy drug therapy administration windows include  $\pm 3$  days for each agent.

dEnd of Tx: End of treatment assessments to be performed within 7 days after last day drug administration or within 7 days after decision to end treatment. Assessments may continue for ongoing reportable adverse events.

e30-Day Post Drug: A contact/visit is to be performed at 30 days (+/-5 days) after the last study drug is given. This may be performed via documented phone conversation with a study nurse or clinician or a clinic visit. All participants will be followed until resolution or stabilization of any serious or reportable adverse events occurring during treatment or starting within 30 days of last study drug.

fActive Follow Up: In participants who discontinue study treatment without documented disease progression, every effort should be made to continue monitoring their disease status by radiologic imaging every 6 weeks (+/- 7 days) until (1) the start of new anti-cancer treatment, (2) documented disease progression, or (3) death whichever occurs first.

gLong Term Follow Up: participants will be followed every 3 months (+/- 1 month) via contact or medical record review until death for post-treatment therapies, reason for stopping those therapies and survival.

hInformed Consent: Informed Consent may be obtained within 28 days of start of study treatment

iInclusion/Exclusion Criteria: source documentation providing investigator's confirmation that the participant had met all eligibility criteria must be available prior to registration.

jDemographics and Medical History: to include review of treatment history for cancer, any ongoing medical conditions and medical history pertaining to eligibility on study and involvement during study.

kConcomitant medications and reason for administration should be documented in the case history from within 28 days before starting study treatment up to the 30-Day Post Drug Visit.

lAdverse event assessment: adverse events experienced by participants will be collected and recorded from the first dose of study treatment up to the 30-Day Post Drug Visit of the last dose of study medication (+/- 5 days depending on when 30-Day Post Drug visit/contact occurs) and all SAEs (related and unrelated to trial treatment) / ECIs up to 90 days after the last dose of trial

mFull Physical Exam (including neurologic exam): to be completed by the investigator or qualified designee at screening, C1D1 and start of all subsequent cycles.

nVital signs: weight, heart rate, blood pressure, respiration rate, temperature. Vital signs must be performed prior to administration of treatment on treatment days. Height required only at screening.

oPerformance Status: See Appendix A for ECOG scale.

pPregnancy Test: For women of child bearing potential, a urine pregnancy test should be performed within 72 hours of first dose of study treatment. If urine pregnancy results are positive or cannot be confirmed as negative, a serum pregnancy test will be required.

qCoagulation – PT/INR, PTT required at screening only.

rHematology: erythrocytes (RBC), hemoglobin, hematocrit, platelets, total WBC plus differential (neutrophils/ANC, lymphocytes, monocytes, eosinophils, basophils).

sSerum Chemistry: albumin, alkaline phosphatase (ALP), bicarbonate (HCO3), BUN, calcium, chloride, creatinine, glucose, lactate dehydrogenase (LDH) magnesium, phosphorous, potassium, SGOT (AST), SGPT (ALT), sodium, total protein, total bilirubin (if total bilirubin is greater than the upper limit of normal, direct should be performed), and uric acid.

tTSH will be performed at baseline, week 1, beginning of cycle 2 and then every 2 cycles. TSH results do not need to be back prior to dosing

uBrain MRI will be performed every 2 cycles. In the rare circumstance where patients have extracranial metastases, chest/abd/pelvis CT will also be obtained every 2 cycles. If pembrolizumab is held or interrupted, the scan schedule should be maintained at every 2 cycles.

vAs per section 5.12, completed 24 months of uninterrupted treatment with pembrolizumab or 35 administrations of study medication, whichever is later

wTissue collected as part of clinical care (e.g. from prior biopsy, craniotomy) will be collected. Tissue needs to be submitted within 30 days after patient enrollment. See Section 9 for specimen collection requirements

xBlood will be collected at screening every 2 cycles (two 10 mL EDTA/lavender top tube) and at the end of treatment

## 11. MEASUREMENT OF EFFECT

### 11.1 Antitumor Effect – Intracranial Disease

For the purposes of this study, participants should be re-evaluated for intracranial response every 6 weeks. In addition to a baseline scan, confirmatory scans should also be obtained at 6 weeks following initial documentation of objective response. Response and progression will be evaluated in this study using the modified RANO Response Criteria.

#### 11.2 Definitions

Evaluable for objective response. Only those participants who have measurable CNS disease present at baseline, have received at least one cycle of therapy, and have had their disease re-evaluated will be considered evaluable for target disease response. These participants will have their response classified according to the definitions stated below. (Note: Participants who exhibit objective disease progression prior to the end of cycle 1 will also be considered evaluable.)

Evaluable non-measurable evaluable disease. Participants who have lesions present at baseline that are evaluable but do not meet the definitions of measurable disease, have received at least one cycle of therapy, and have had their disease re-evaluated will be considered evaluable for non-target disease. The response assessment is based on the presence, absence, or unequivocal progression of the lesions.

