### 11.3 Response Criteria

#### 11.3.1.1 Evaluation of Intracranial Lesions

Complete Response (CR): Requires all of the following:

- complete disappearance of all enhancing measurable and nonmeasurable disease sustained for at least 4 weeks
- no new lesions
- stable or decreasing corticosteroids (the steroid dose at the time of the scan evaluation should be no greater than the dose at time of baseline scan)
- stable or improved clinically

*Participants with non-measurable disease cannot have a complete response. The best possible response is stable disease.*

Partial Response (PR): All of the following criteria must be met:

- Greater than or equal to 50% decrease compared to baseline in the sum of products of perpendicular diameters of all measurable enhancing lesions sustained for at least 4 weeks. In the absence of a confirming scan 4 weeks later, this scan will be considered only stable disease.
- no progression of non-measurable disease.
- no new lesions
- stable or reduced corticosteroid dose (the steroid dose at the time of the scan evaluation should be no greater than the dose at time of baseline scan)
- stable or improved clinically

Progressive Disease (PD): At least one of the following must be true:

- $\geq 25\%$  increase in the sum of products of all measurable lesions over smallest sum observed (over baseline if no decrease) using the same techniques as baseline
- clear worsening of any nonmeasurable disease\*
- appearance of any new enhancing lesion/site
- clear clinical worsening (unless clearly unrelated to this cancer, e.g. seizures, medication side effects, complications of therapy, cerebrovascular events, infection)
- failure to return for evaluation due to death or deteriorating condition

\* Progression of non-measurable CNS lesions is defined as follows:

- a lesion initially at baseline  $\leq 5$ mm in diameter that increases to  $\geq 10$ mm in diameter, or
- a lesion initially at baseline 6-9 mm in diameter that increases by at least 5 mm in diameter.
- a lesion that is smaller than 10mm that is too complex or has poorly defined margins, that is now unequivocally progressing by more than 25%

Stable Disease (SD): All of the following criteria must be met:

- Does not qualify for CR, PR or progression
- All measurable and non-measurable sites must be assessed using the same techniques as baseline
- Stable clinically.

A summary of the response criteria is in the below:

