#### 11.4.1 Definitions

Evaluable for Target Disease response. Only those participants who have measurable disease present at baseline, have received at least one cycle of therapy, and have had their disease re-evaluated will be considered evaluable for target disease response. These participants will have their response classified according to the definitions stated below. (Note: Participants who exhibit objective disease progression prior to the end of cycle 1 will also be considered evaluable.)

Evaluable Non-Target Disease Response. Participants who have lesions present at baseline that are evaluable but do not meet the definitions of measurable disease, have received at least one cycle of therapy, and have had their disease re-evaluated will be considered evaluable for non-target disease. The response assessment is based on the presence, absence, or unequivocal progression of the lesions.

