### **13.7 Analysis of Secondary Endpoints**

Safety and Tolerability: All adverse events recorded during the trial will be summarized for all patients having received one or more doses of pembrolizumab. The proportions of patients with grade-3 or higher hematologic toxicities or grade-3 or higher neurologic toxicities will be presented with 90% exact binomial confidence intervals. The incidence of events that are new or worsening from the time of first dose of treatment will be summarized according to system organ class and/or preferred term, severity (based on CTCAE grade), type of adverse event, and relation to study treatment. Deaths reportable as SAEs and non-fatal serious adverse events will be listed by patient and tabulated by primary system organ class, and type of adverse event.

Overall Survival: The distributions of overall survival will be summarized using the method of Kaplan-Meier. The follow-up of patients who are alive at the time of analysis will be censored at the date of last assessment of vital status. Median OS will be presented and accompanied by 90% confidence intervals estimated using log(-log(survival)) methodology. Survival point estimates at 3 and 6 months will also be presented with confidence intervals.

Intracranial/Extracranial Response: Contrast-enhanced cranial magnetic resonance imaging (MRI) will be performed every 6 weeks. The proportion of patients with intracranial response (CR, PR or SD by RANO) will be presented with a two-sided, 90% exact binomial confidence interval.

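### Section 13.7 names no denominator for the response proportion; on the natural reading Section 11.2 supplies one that drops treated patients who fail before any re-evaluation, which can only raise the rate

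*Combined protocol and SAP*

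**What the plan says.** Section 11.2 defines who is evaluable for objective intracranial response: patients with measurable CNS disease at baseline who "have received at least one cycle of therapy, and have had their disease re-evaluated will be considered evaluable for target disease response". It continues: "These participants will have their response classified according to the definitions stated below". Its only exception is a note: "Participants who exhibit objective disease progression prior to the end of cycle 1 will also be considered evaluable". Section 11.4.1 repeats the restriction for extracranial disease: "Only those participants who have measurable disease present at baseline, have received at least one cycle of therapy, and have had their disease re-evaluated".

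Section 11.3.1.1 lists two PD criteria that need no scan: "clear clinical worsening (unless clearly unrelated to this cancer", and "failure to return for evaluation due to death or deteriorating condition". Section 11.1 sets the timing: "participants should be re-evaluated for intracranial response every 6 weeks".

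Section 13.7 gives the analysis of this secondary endpoint: "The proportion of patients with intracranial response (CR, PR or SD by RANO) will be presented", with a two-sided 90% exact binomial interval. It does not say which patients form the denominator.

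The sets stated elsewhere serve other endpoints. Section 13.2 (patients who began treatment) and Section 13.9.2 (at least one cycle) cover the primary endpoint, and Section 13.9.1 (at least one dose) covers toxicity. None of them requires re-evaluation.

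**The concern.** Sections 11.2 and 11.3.1.1 treat the same patient differently. Someone who completes cycle 1 and dies or declines before the 6-week MRI, with no re-evaluation, has PD under Section 11.3.1.1 but is never classified under Section 11.2. The note in Section 11.2 does not recover this patient, because it covers only objective progression before the end of cycle 1. A death or clinical decline without objective progression during cycle 1 is not covered either. Patients who withdraw or are lost before any re-evaluation also drop out of the set.

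This exclusion depends on outcome. The patients removed cannot be responders, so removing them moves the estimate and both interval limits in one direction. What is at stake is the third secondary objective in Section 1.3, the response rate. Section 13.7 counts SD along with CR and PR, so the reported figure is a disease-control proportion, and early failures without a scan are its clearest failures. With about 24 patients, one or two exclusions visibly move the result.

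**Working it through.** **The plan's own figure.** The documents give no number for the response analysis. The nearest one is the primary rule in Section 13.6: at least 10 successes in 24, 26% versus 52%, one-sided level 0.1, power at least 88%. Exact binomial: P(X ≥ 10 | n = 24, p = 0.52) = 0.888 and P(X ≥ 10 | n = 24, p = 0.26) = 0.069. The stated power is reproduced, and nothing below changes it.

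**Direction.** Let N be the treated patients with measurable disease, x those with CR, PR or SD, and d those dropped because they were never re-evaluated. CR and PR need a follow-up scan, and SD under Section 11.3.1.1 needs all sites assessed with the baseline technique. A patient never re-evaluated is therefore not in x. The rate moves from x/N to x/(N − d), a relative increase of N/(N − d) − 1, which is positive whenever d > 0 and x > 0.

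**Size.** Neither d nor x is in the documents; both are assumed. Take N = 24 and d = 1 to 3. Let x = 15 illustrate CR/PR/SD and x = 2 illustrate a count of CR and PR only. Intervals are Clopper-Pearson 90%.

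| d | Relative increase | x = 15 | x = 2 |
|---|---|---|---|
| 0 | 0 | 15/24 = 62.5% (43.7–78.8) | 2/24 = 8.3% (1.5–24.0) |
| 1 | 24/23 − 1 = 4.3% | 15/23 = 65.2% (45.9–81.4) | 2/23 = 8.7% (1.6–24.9) |
| 2 | 24/22 − 1 = 9.1% | 15/22 = 68.2% (48.4–84.0) | 2/22 = 9.1% (1.6–25.9) |
| 3 | 24/21 − 1 = 14.3% | 15/21 = 71.4% (51.3–86.8) | 2/21 = 9.5% (1.7–27.1) |

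The absolute shift is 2.7 to 8.9 points for x = 15 and 0.4 to 1.2 points for x = 2.

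**Why the range stops at 3.** Assume a constant hazard over 6 months (26.09 weeks). A 26% PFS6 gives h = −ln(0.26)/26.09 = 0.0516 per week. The share with a PFS event between weeks 3 and 6 is exp(−3h) − exp(−6h) = 0.857 − 0.734 = 0.123, or 2.9 of 24. At 52% PFS6, h = 0.0251 and the share is 0.928 − 0.860 = 0.067 after rounding, or 1.6 of 24. These count every PFS event, including progression found by a scan, and those patients are not dropped. They leave out weeks 0 to 3 and non-PFS dropouts. They set a scale and do not estimate d.

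**The case against.** **The denominator is inferred.** Section 13.7 speaks of patients and does not refer to Section 11.2. A reader might infer that the plan expressly prescribes a re-evaluated-only denominator; it does not. This stands as a limit on the claim. But Section 11.2 is the only response-evaluable definition for intracranial disease, and if all treated patients were intended, Section 13.7 still has to say so.

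**Most toxicity stops are scanned.** A reader might infer that everyone who stops early for toxicity is lost. The Section 10 calendar does not support that. Tumor imaging is scheduled at discontinuation (within 7 days, note d), imaging continues every 6 weeks after stopping without progression (note f), and scans stay on schedule when drug is held (note u). The gap is therefore confined mainly to deaths, patients too unwell to be scanned, withdrawals and losses.

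**Re-evaluation need not mean MRI.** A physical and neurologic examination is planned every cycle, and clear clinical worsening is itself PD. A patient who declines at the cycle 2 visit could be read as re-evaluated. That is reasonable and narrows the conflict, but Section 11.2 does not say so, and it does nothing for a patient who never comes back. The failure-to-return rule works normally for anyone assessed at least once.

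**The effect may be small.** A reader might take 3 of 24 as the expected loss. The documents do not support that, because the 12.3% behind it includes progressions found by scan. The endpoint is also descriptive, with no test or decision rule. Both points limit the importance of the finding but leave its direction unchanged.

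**Conclusion.** The point holds in a limited form. Section 11.2 conflicts with Section 11.3.1.1 for patients who fail before any re-evaluation, and Section 13.7 does not settle which rule sets the denominator. Applied as they most naturally read, the sections can only overstate the CR/PR/SD proportion. The direction is certain if any treated patient is dropped this way while at least one patient responds. The size is not known from the documents: with 1 to 3 of 24 dropped, it is about 3 to 9 points on a proportion near 62.5% and about 1 point or less on one near 8.3%.

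A reader might go further and infer that the main result is biased. It is not: neither primary-endpoint set requires re-evaluation, so PFS6, the 10-of-24 rule and its power stand. This should be corrected before analysis, as a matter of wording in a secondary endpoint.

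**What to change.** 1. In Section 13.7, state that the denominator is all patients who received at least one dose and had measurable disease at baseline. Count anyone without a post-baseline assessment as a non-responder, and as PD where the reason is death or deterioration, in line with Section 11.3.1.1.
2. In Sections 11.2 and 11.4.1, remove both the one-cycle and the re-evaluation conditions as far as the rate is concerned. Removing only the second would leave a one-cycle rule in conflict with the one-dose denominator in Section 13.7.
3. Report the evaluable-only rate as a sensitivity analysis, with the number excluded and the reasons.

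The cost is wording only: no extra patients, visits or data. The reported proportion becomes slightly lower. Settling the rule before analysis also removes a choice of denominator after the results are known.
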